This protocol has been approved by:**Name:** [name]**Trial Role:** Chief Investigator**Signature:****Date:**15 / Aug /2018

This protocol describes the AVAIL-T trial and provides information about procedures for patients taking part in the AVAIL-T trial. The protocol should not be used as a guide for treatment of patients not taking part in the AVAIL-T trial.

AMENDMENTS

The following amendments and/or administrative changes have been made to this protocol since the implementation of the first approved version

Amendment number	Date of amendment	Protocol version number	Type of amendment	Summary of amendment
1	25-May-2017	2.0	Substantial	Removal of one form of contraception from section 5.3
2	29-Aug-2017	3.0	Substantial	Section 7.5 Dose Modifications updated with new information provided in Avelumab IV V7.0 Clarification of patient registration processes.
3	20-Feb-2018	4.0	Substantial	Change to inclusion criteria: 
hepatosplenic T-cell lymphoma removed as a PTCL histology for safety reasonschange to hepatic function criteria for safety reasonsaddition of a PTCL histology Clarification of pregnancy tests (in screening and assessments sections (5.1 and 7.2) Clarification of treatment details in section 7.1 Clarification of management of IRRs in section 7.5 (Table 3)

				Clarification of management of Hepatic AEs (Table 4) Clarification of treatment discontinuation section (Table 5) Clarification of research sample collection Contact details updated
4	04-May-2018	5.0	Substantial	Update to treatment section – mandate dose banding for avelumab Clarification of post screening pregnancy tests (section 7.2) Clarification of steroid use in the concomitant medication section Update to research sample collection – addition of technique used for immunophenotyping Update to Table 5 to ensure it is consistent with guidance in Table 3
N/A	15-Aug-2018	5.0a	Notification	Change in Data Protection Regulations

TRIAL SYNOPSIS

Title

AVAIL-T: A Phase 2a trial of Avelumab, an anti-PD-L1 antibody, in relapsed and refractory peripheral T-cell lymphoma (PTCL)

Trial Design

This is a multicentre, single arm, open-label, phase 2a trial to determine responses to avelumab, an anti-PD-L1 antibody, in patients with refractory and relapsed PTCL. A single arm study has been selected to determine evidence of activity in PTCL to further evaluate in a larger trial.

Objectives

The primary objective of the trial is to determine overall response during 8 cycles of treatment with secondary objectives being toxicity, overall survival (OS), progression free survival (PFS), radiological reduction in tumour size and duration of response from time of first documented response until relapse, progression or death.

Outcome Measures

Primary Outcome Measures

- Best overall response (Partial Remission (PR) + Complete Response (CR)) during 8 cycles of treatment using Revised Response Criteria for Malignant Lymphoma (Appendix 1)

Secondary Outcome Measures

- Toxicity assessed using the National Cancer Institute Common Terminology Criteria for Adverse Events (NCI CTCAE) version 4
- Best overall response (PR + CR) at any time of treatment using Revised Response Criteria for Malignant Lymphoma²⁷
- OS
- PFS
- Reduction in tumour size measured as maximum percentage change in the radiological sum of the product of the diameters from baseline of up to 6 target lesions
- Duration of response from time of first documented response until relapse, progression or death

Exploratory Outcome Measures

- PD-L1 expression levels
- Cell free DNA analysis
- Immunophenotyping
- Biomarkers of response

Patient Population and Sample Size

This trial will recruit 30-35 patients with relapsed or refractory PTCL.

Main Inclusion Criteria

- Male or female patients aged ≥ 16 years
- Life expectancy > 12 weeks
- ECOG performance status ≤ 2
- Relapsed or refractory* peripheral T-cell lymphoma including the following histologies: peripheral T-cell lymphoma not otherwise specified (PTCL NOS) , angioimmunoblastic T-cell

lymphoma (AITL), anaplastic large cell lymphoma (ALCL), enteropathy associated T-cell lymphoma (EATL), extranodal NK/T- cell lymphoma (ENKL), transformed mycosis fungoïdes (LCT MF), and subcutaneous panniculitis and T cell lymphoma * For all relapsed patients, relapse must be confirmed by tissue biopsy (or bone marrow trephine if no other tissue available). For relapsed and refractory patients, a biopsy must have been obtained within the last 3 months of registration

- Failed at least 1 prior therapy (but no upper limit of prior regimens)
- Adequate haematological function defined by the following at registration:
 - absolute neutrophil count (ANC) $\geq 1.0 \times 10^9/L$ (unsupported)
 - platelet count $\geq 75 \times 10^9/L$ (unsupported)
 - haemoglobin $\geq 90 \text{ g/L}$ (may have been transfused)
- Adequate hepatic function and no evidence of hepatic involvement by T-cell lymphoma as defined by:
 - total bilirubin level $\leq 1.5 \times$ the upper limit of normal (ULN) range (patients with elevated bilirubin due to Gilbert's syndrome are eligible)
 - AST and ALT levels $\leq 1.5 \times$ ULN for all patients **and**
 - no clinical suspicion of hepatic involvement by T-cell lymphoma and
 - no liver abnormalities on imaging studies that might be due to T-cell lymphoma
- Adequate renal function defined by an estimated creatinine clearance $\geq 30 \text{ mL/min}$ according to the Cockcroft-Gault formula (or local institutional standard method)
- CT measurable disease with at least 1 lesion having short axis $> 1.5\text{cm}$ or splenomegaly $> 14\text{cm}$ in cranio-caudal length attributable to relapsed/non responding lymphoma
- Negative serum pregnancy test at screening for women of childbearing potential.
- Highly effective contraception for both male and female patients if the risk of conception exists. (Note: women of childbearing potential and men able to father a child must agree to use 2 highly effective contraception, defined as methods with a failure rate of less than 1 % per year. Highly effective contraception is required from consent, throughout and for at least 60 days after avelumab treatment.
- Ability to give informed consent

Main Exclusion Criteria

Patients are not eligible for the trial if they fulfill any of the following exclusion criteria:

- All patients with active CNS involvement of lymphoma
- Prior organ transplantation, including allogeneic stem-cell transplantation
- Significant acute or chronic infections including, among others:
 - Known history of testing positive test for human immunodeficiency virus (HIV) or known acquired immunodeficiency syndrome (AIDS),
 - Hepatitis B virus (HBV) or hepatitis C virus (HCV) infection at screening (positive HBV surface antigen or HCV RNA if anti-HCV antibody screening test positive)
- Current use of immunosuppressive medication, EXCEPT for the following:
 - intranasal, inhaled, topical steroids, or local steroid injection (e.g., intra-articular injection); Systemic corticosteroids at a maximum dose of $\leq 1 \text{ mg/kg}$ of prednisone or equivalent during screening (to be stopped by day 1 of trial treatment); Steroids as premedication for hypersensitivity reactions (e.g., CT scan premedication).
- Active autoimmune disease that might deteriorate when receiving an immunostimulatory agent. Patients with diabetes type I, vitiligo, psoriasis, hypo- or hyperthyroid disease not requiring immunosuppressive treatment are eligible
- Known prior severe hypersensitivity to investigational product or any component in its formulations, including known severe hypersensitivity reactions to monoclonal antibodies (NCI CTCAE v4.03 Grade ≥ 3)

- Persisting toxicity related to prior therapy of Grade >1 NCI-CTCAE v 4.03; however, alopecia and sensory neuropathy Grade ≤ 2 or other Grade ≤ 2 not constituting a safety risk based on investigator's judgment are acceptable
- Pregnancy or lactation
- Known alcohol or drug abuse
- Clinically significant (i.e., active) cardiovascular disease: cerebral vascular accident/stroke (< 6 months prior to registration), myocardial infarction (< 6 months prior to registration), unstable angina, congestive heart failure (\geq New York Heart Association Classification Class II), or serious cardiac arrhythmia requiring medication
- Other severe acute or chronic medical conditions including colitis, inflammatory bowel disease, pneumonitis, pulmonary fibrosis or psychiatric conditions including recent (within the past year) or active suicidal ideation or behaviour; or laboratory abnormalities that may increase the risk associated with study participation or study treatment administration or may interfere with the interpretation of study results and, in the judgment of the investigator, would make the patient inappropriate for entry into this study
- Vaccination within 4 weeks of the first dose of avelumab and while on trial is prohibited except for administration of inactivated vaccines (e.g. the flu vaccine)
- Active infection requiring systemic therapy
- Major surgery within 4 weeks of trial entry
- Patients and partners of childbearing potential not willing to use two methods of effective contraception during and for 60 days after therapy

Trial Duration

Patients will be recruited over 24 months from 13 Trials Acceleration Programme (TAP) and non-TAP centres.

Following registration, patients will receive 8 cycles (each of 28 days duration) of avelumab (each cycle being two, fortnightly infusions of the antibody) with the possibility of continued treatment if the patient is benefitting. The patient will have an end of treatment visit within 28 days of the end of the last cycle.

A contrast enhanced CT scan of the neck, chest, abdomen and pelvis will be performed at cycles 3, 6 and 8 of treatment to assess response during treatment. If the patient has not progressed after 8 cycles they will continue to be followed up with CT scans at 12, 16 and 20 months from treatment start or sooner if the Investigator is concerned there may be disease progression or if the patient discontinues treatment. After 20 months from treatment start, radiological follow-up will be as per local standard with data collected every 6 months.

Patients will continue to be followed up for progression and survival until the end of trial.

Trials Office Contact Details

AVAIL-T trial team
Centre for Clinical Haematology
Queen Elizabeth Hospital
[name]
[contact]
[contact]
Email: [contact]

ABBREVIATIONS

ABPI	ASSOCIATION OF THE BRITISH PHARMACEUTICAL INDUSTRY
ACTH	ADRENOCORTICOTROPIC HORMONE
ADCC	ANTIBODY DEPENDENT CELLULAR CYOTOXICITY
ADL	ACTIVITIES OF DAILY LIVING
AE	ADVERSE EVENT
AHA	AMERICAN HEART ASSOCIATION
AIDS	ACQUIRED IMMUNODEFICIENCY SYNDROME
AITL	ANGIOIMMUNOBLASTIC LYMPHOMA
ALCL	ANAPLASTIC LARGE CELL LYMPHOMA
ALP	ALKALINE PHOSPHATASE
ALT	ALANINE TRANSAMINASE
AML	ACUTE MYELOID LEUKEMIA
ANC	ABSOLUTE NEUTROPHIL COUNT
AR	ADVERSE REACTION
AST	ASPARTATE TRANSAMINASE
CR	COMPLETE REMISSION/RESPONSE
CrCL	CREATININE CLEARANCE
CRCTU	CANCER RESEARCH UK CLINICAL TRIALS UNIT (UNIVERSITY OF BIRMINGHAM)
CRF	CASE REPORT FORM
CRP	C-REACTIVE PROTEIN
CR UK	CANCER RESEARCH UK
CT	COMPUTER TOMOGRAPHY
CTC	COMMON TERMINOLOGY CRITERIA
CTCAE	COMMON TERMINOLOGY CRITERIA FOR ADVERSE EVENTS
CTCL	CUTANEOUS T-CELL LYMPHOMA
CV	CURRICULUM VITAE
DCF	DATA CLARIFICATION FORM
DNA	DEOXYRIBOSE NUCLEIC ACID
EATL	ENTEROPATHY ASSOCIATED T-CELL LYMPHOMA
ECG	ELECTROCARDIOGRAM
ECMC	EXPERIMENTAL CANCER MEDICINE CENTRE
ECOG	EASTERN COOPERATIVE ONCOLOGY GROUP
EDC	ELECTRONIC DATA CAPTURE
EMEA	EUROPEAN MEDICINES AGENCY
ENKL	EXTRANODAL NK/T- CELL LYMPHOMA
EORTC	EUROPEAN ORGANISATION FOR RESEARCH AND TREATMENT OF CANCER
ESC	EUROPEAN SOCIETY OF CARDIOLOGY
FBC	FULL BLOOD COUNT
FDA	(USA) FOOD AND DRUG ADMINISTRATION
FSH	FOLLICLE-STIMULATING HORMONE
GCP	GOOD CLINICAL PRACTICE

GGT	GAMMA-GLUTAMYL TRANSPEPTIDASE
GMP	GOOD MANUFACTURING PRACTICE
GP	GENERAL PRACTITIONER
HBV	HEPATITIS B VIRUS
HCG	HUMAN CHORIONIC GONADOTROPHIN
HCV	HEPATITIS C VIRUS
HGB	HAEMAGLOBIN
HIV	HUMAN IMMUNODEFICIENCY VIRUS
IB	INVESTIGATOR BROCHURE
ICF	INFORMED CONSENT FORM
ICOS	INDUCIBLE CO-STIMULATOR

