7.2 Treatment Schedule

Avelumab 10 mg/kg will be administered once every 14 days for a proposed duration of 8 cycles (28 day cycles), (16 doses).

If the patient is showing clinical benefit following 8 cycles of trial treatment patients may continue to receive avelumab treatment at the treating Investigator's discretion, until loss of response, toxicity, or death.

Every effort should be made for patients to attend on the scheduled visit days. However, if a patient is unable to attend on the specified day, assessments may be scheduled for +/- 3 days.

The full blood count should be assessed prior to each treatment (within 24 hours of treatment) to ensure the following criteria are met:

- Platelets $> 75 \times 10^9/L$
- Neutrophils $> 1.0 \times 10^9/L$
- Bilirubin $< 1.5 \times ULN$
- Creatinine clearance (CrCL) (Cockcroft-Gault) $\geq 30 \text{ ml/min}$.
- ALT/AST $\leq 1.5 \times ULN$ on Cycle 1 day1; thereafter $\leq 3 \times ULN$

Please also refer to Section 7.5 for dose delays and modifications, and to section 7.7 for concomitant medications.

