7.3.1 Blood chemistry and Haematology

Full Blood count (Haemoglobin, Platelets, WBC, Neutrophils and Lymphocytes) and serum biochemistry (to include AST/ALT, Alkaline phosphate, bilirubin, Calcium (adjusted), Creatinine, Creatinine Clearance, C-Reactive Protein, Magnesium, Potassium, Sodium, GGT, Phosphate, and glucose -non fasted) will be taken within the 24h prior to each avelumab dose and at the End of Treatment visit .

Triglycerides and Cholesterol should also be assessed at Cycle 4 day 1 and End of Treatment visit only

Hormone function tests (ACTH, Free T4, and TSH) and tests for pancreatitis (such as Amylase and or Lipase as per institutional standard) will be performed prior to avelumab infusion where possible on Cycle 1 Day 1, Cycle 3 day 1, Cycle 5 day 1, Cycle 7 day 1, and at the End of treatment visit (if not performed in the previous 8 weeks). Test should additionally be performed in cases of suspected hypoadrenalism, hypopituitarism or pancreatitis.

Pregnancy test - For female patients of childbearing potential, a serum pregnancy test, with sensitivity of at least 25 mIU/mL and assayed in a certified laboratory, once at the start of screening. Urine or serum pregnancy tests will be routinely repeated at every treatment cycle during the active treatment period (immediately before investigational product administration) and at the end of study treatment visit. Additionally whenever 1 menstrual cycle is missed or when potential pregnancy is otherwise suspected this test should be repeated.

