7.5.6 Drug Induced Liver Injury (Hy's law cases)

The threshold of laboratory abnormalities for a potential Drug Induced Liver Injury case depends on the patient's individual baseline values and underlying conditions. Patients who present with the following laboratory abnormalities should be evaluated further as potential Hy's law cases to definitively determine the etiology of the abnormal laboratory values:

-Subjects with AST/ALT and Bilirubin baseline values within the normal range who subsequently present with AST OR ALT values $>3 \times$ ULN AND a Bilirubin value $>2 \times$ ULN with no evidence of hemolysis and an alkaline phosphatase value $<2 \times$ ULN or not available;

-For subjects with baseline AST OR ALT OR Bilirubin values above the ULN, the following threshold values are used in the definition mentioned above, as needed, depending on which values are above the ULN at baseline:

- Preexisting AST or ALT baseline values above the normal range: AST or ALT values >2 times the baseline values AND $>3 \times$ ULN; or $>8 \times$ ULN (whichever is smaller).
- Preexisting values of Bilirubin above the normal range: Bilirubin level increased from baseline value by an amount of at least $1 \times$ ULN or if the value reaches $>3 \times$ ULN (whichever is smaller).

If a Hy's law case is confirmed this must be reported to the trials office as an SAE. Patients should be treated as in Table 4 above.

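### Entry admits patients with raised bilirubin from Gilbert's syndrome, but the 7.2 pre-dose limit and Table 4 carry no such exemption, so read literally some eligible patients could not be dosed

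*Combined protocol and SAP*

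**What the plan says.** **Entry (synopsis and 4.1, same text).** Total bilirubin must be no more than 1.5 x ULN, but "patients with elevated bilirubin due to Gilbert's syndrome are eligible". No upper limit is given for those patients. Creatinine clearance must be at least 30 mL/min "according to the Cockcroft-Gault formula (or local institutional standard method".

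**Before each dose (7.2).** Blood results "should be assessed prior to each treatment (within 24 hours of treatment) to ensure the following criteria are met". The list requires bilirubin strictly below 1.5 x ULN, with no mention of Gilbert's syndrome. The renal line keeps the 30 mL/min limit and reads "Creatinine clearance (CrCL) (Cockcroft-Gault", with no local alternative. The ALT/AST line has one limit "on Cycle 1 day1; thereafter" a looser one (1.5 x ULN, then 3 x ULN). Section 7.3.1 confirms that chemistry, including bilirubin and creatinine clearance, "will be taken within the 24h prior to each avelumab dose"; it names no clearance method.

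**During treatment (Table 4, hepatic rows).** Bilirubin above ULN and up to 1.5 x ULN is Grade 1: continue. Above 1.5 and up to 3 x ULN is Grade 2: withhold avelumab and give prednisolone 1.0 to 2.0 mg/kg/day; if this lasts beyond 5 to 7 days, treat as Grade 3 to 4. Grade 3 to 4 (above 3 x ULN) means permanent discontinuation. No row mentions Gilbert's syndrome or baseline.

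**Hy's law evaluation (7.5.6).** Here the plan does allow for a raised baseline: "Preexisting values of Bilirubin above the normal range: Bilirubin level increased from baseline value" by at least 1 x ULN, or a value above 3 x ULN, whichever is smaller.

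**Analysis (12.2).** The response rate is taken over all registered patients, and those who cannot be assessed are non-responders. The per protocol set needs eligibility and at least one dose.

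**The concern.** The exemption matters only for patients above 1.5 x ULN, since anyone at or below that level meets the entry limit without it. Those are the patients whom 7.2 stops from being dosed. A pre-dose limit can reasonably be stricter than entry in order to catch deterioration. Here it would fail a patient at a stable, accepted baseline before any drug has been given.

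At stake is a dosing deviation, a site-by-site reading of the rule, or a registered patient who is never treated and then counts against the drug because of wording and not because of any clinical change. Applied literally, Table 4 would also expose the patient to steroids for a long-standing benign finding.

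**Working it through.** The plan states no figure on this point, so the check sets the rules side by side. The bilirubin values are illustrative, assumed stable, in a patient with Gilbert's syndrome and raised baseline bilirubin. The 7.5.6 column is the smaller of (baseline + 1 x ULN) and 3 x ULN.

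| Bilirubin (x ULN) | Entry | 7.2 | Table 4 | 7.5.6 bilirubin threshold |
|---|---|---|---|---|
| 1.4 | within limit | pass | Grade 1, continue | 1.4 + 1 = 2.4 |
| 1.5 | within limit | fail (limit is strict) | Grade 1, continue | 1.5 + 1 = 2.5 |
| 1.6 | by exemption only | fail | Grade 2, withhold and steroids | 1.6 + 1 = 2.6 |
| 2.0 | by exemption only | fail | Grade 2, withhold and steroids | 2.0 + 1 = 3.0 |
| 3.5 | by exemption only | fail | Grade 3 to 4, stop permanently | 3 (already exceeded) |

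Four things follow.

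1. Every patient who needs the exemption (above 1.5 x ULN) fails 7.2 at each dose for as long as the value stays there. Cycle 1 day 1 is included, because the check applies before every treatment.
2. Nothing lifts this elsewhere. Section 7.2 points to 7.5 and 7.7; neither mentions Gilbert's syndrome, which is named only in the two eligibility lists.
3. Correcting 7.2 alone would not be enough. At 2.0 x ULN, a dose that 7.2 then allowed would still be withheld under Table 4, and persistence beyond 5 to 7 days would move the patient to permanent discontinuation.
4. The plan has suitable wording to hand. The ALT/AST line in 7.2 is matched to entry at cycle 1 day 1, and 7.5.6 measures bilirubin against baseline. Section 7.5.6 triggers an evaluation and is not a dosing rule, but it shows that raised baseline bilirubin was considered there.

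**Creatinine clearance.** The limit is 30 mL/min in both places and Cockcroft-Gault is the method named first in both. The texts diverge only for a patient whose local result and Cockcroft-Gault result fall on opposite sides of 30.

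**Consequence under 12.2.** An undosed patient remains among the registered patients, counts as a non-responder if not assessable, and drops out of the per protocol set.

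**The case against.** The best defence is that 7.2 may be deliberately cautious. It agrees closely with Table 4, and the amendment log shows that hepatic entry criteria were changed for safety and the hepatic management rows clarified. Section 7.2 also does not say that a patient who fails is never treated: it refers to 7.5 for delays, 7.1 says that all registered patients will receive avelumab, and Table 4 tells sites to contact the chief investigator and trials office about liver concerns. A sensible investigator would probably not treat stable Gilbert's syndrome as an immune-related event, and 8.1.1 asks for pre-existing conditions to be reported only if they worsen.

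Much of this stands. The documents do not show whether the missing exemption is oversight or intent, and permanent non-treatment is an inference. But if caution was intended, the entry exemption has no use above 1.5 x ULN, which is the only place where it could have any. Investigator discretion under 4.2 to exclude risky laboratory abnormalities does not reconcile the texts either, because these patients are expressly called eligible.

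Two stronger readings are tempting. A reader might infer that the creatinine wording is an equal conflict. It is not: the limit is the same, and because 7.3.1 names no method, a site could reasonably carry its entry method forward. A reader might also infer that the primary result is distorted. With a Beta(1,1) prior (assumed for the plan's uninformative prior), P(rate > 35%) = 1 - BetaCDF(0.35; 1 + x, 1 + n - x). This gives 60.3% for 11 of 30, matching the plan's 60%, and 65.5% for 11 of 29 if one undosed patient is dropped. That gap arises with any undosed patient, whatever the cause, between two analysis sets that the plan already reports. It does not measure this problem.

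**Conclusion.** The bilirubin conflict is real on the text and minor in consequence. Following the plan literally would withhold drug from a patient it declares eligible, provided that the patient's bilirubin stays at or above 1.5 x ULN; a patient with Gilbert's syndrome below that level is unaffected. The count as a non-responder follows only if the patient is also never assessable.

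The number affected is unknown and may be zero: the documents give no count of patients with Gilbert's syndrome and none of sites using another clearance method, so any probability put on it would be a guess. No stated probability, sample size or interim rule changes. The creatinine wording is close to editorial. The confidence here is in the conflict between the texts, not in any effect on the result.

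**What to change.** In the 7.2 bilirubin line and the Table 4 hepatic bilirubin rows, add that for patients with documented Gilbert's syndrome bilirubin is judged against baseline: for example, no rise of 1 x ULN or more above baseline, and not above 3 x ULN. This is the form that 7.5.6 already uses. For a baseline of 2.0 x ULN, dosing could then continue while bilirubin is below 3.0 x ULN. The clinical team should confirm the cap. Entry sets none for these patients, so whatever cap is chosen should be repeated in the synopsis and 4.1; otherwise a patient above it would again be eligible but undosable.

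Optional: state in 7.2 that the creatinine clearance method used at entry is also used before dosing.

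The cost is a few words and no new test. The downside is a slightly looser pre-dose liver check for these few patients, with the ALT/AST limits unchanged. A cap at entry would narrow eligibility slightly.
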